6.2 Prohibited or Restricted Therapy

The following therapies are prohibited until study treatment has been permanently discontinued:

- Any investigational agent or investigational medical device.
- Any non-protocol systemic anticancer treatment (e.g., chemotherapy, immunotherapy, radionuclides, drugs or herbal products used specifically for the treatment of the cancer under investigation).

- Immunosuppressive agents including immunosuppressive doses of systemic corticosteroids with exceptions as stated in Section 6.1.
- Live vaccines are prohibited while on study and until 5 months after last dose of IO agent (e.g., intranasal influenza, measles, mumps, rubella, oral polio, BCG, yellow fever, varicella, and TY21a typhoid vaccines). The use of inactivated (killed) vaccines for the prevention of infectious disease is permitted.
- Metamizole (dipyrone) because of its potential for causing agranulocytosis.
- Anticoagulants: Prohibits coumarin agents, direct thrombin inhibitors, direct factor Xa inhibitor
 betrixaban, platelet inhibitors, and aspirin above low-dose levels for cardio-protection until 4
 weeks after cabozantinib has been permanently discontinued

The following therapies should be avoided until study treatment has been permanently discontinued or until otherwise specified:

- Local anticancer treatment including palliative radiation, ablation, embolization, or surgery with impact on tumor lesions should not be performed until radiographic progression per RECIST 1.1 has been established.
- Erythropoietic stimulating agents (e.g., epoetin alfa and darbepoetin alfa) should not be used based on a report of increased risk of tumor recurrence/progression associated with erythropoietin²¹.
- Concomitant medications that are known to prolong the QTc interval should be avoided in subjects who receive cabozantinib until they have permanently discontinued cabozantinib treatment (refer to http://www.qtdrugs.org for a list of drugs which have the potential to prolong the QTc interval).
- Chronic co-administration of cabozantinib with strong inducers of the CYP3A4 family
 (e.g., phenytoin, carbamazepine, rifampin, rifabutin, rifapentine, phenobarbital, and St. John's
 Wort) may significantly decrease cabozantinib concentrations and should be avoided. Selection
 of alternate concomitant medications with no or minimal CYP3A4 enzyme induction potential is
 recommended.
- Caution must be used when discontinuing treatment with a strong CYP3A4 inducer in a subject
 who has been concurrently receiving a stable dose of cabozantinib, as this could significantly
 increase the exposure to cabozantinib.

Co-administration of cabozantinib with strong inhibitors of the CYP3A4 family (e.g., boceprevir, conivaptan, posaconazole, ketoconazole, itraconazole, clarithromycin, atazanavir, indinavir, nefazodone, nelfinavir, saquinavir, ritonavir, lopinavir, telaprevir, telithromycin, and voriconazole) may increase cabozantinib concentrations and should be avoided. Grapefruit, star fruit, and Seville oranges may also increase plasma concentrations of cabozantinib and should be avoided.

6.2.1 Potential Drug Interactions with Cabozantinib and Effects of Food

Currently available data suggest that cabozantinib: (1) is not anticipated to markedly induce or inhibit CYP enzymes at clinically-relevant plasma concentrations; (2) is a substrate for CYP3A4; (3) may have the potential to inhibit the P-gp transport activity but is not a substrate of P-gp; and (4) is a substrate of drug transporter MRP2.

Cytochrome P450: Cabozantinib is a CYP3A4 substrate and a weak substrate for CYP2C9 (but not a CYP2D6, CYP2C8, CYP2C19, CYP2B6, or CYP1A2 substrate). Co-administration of cabozantinib with strong inducers of the CYP3A4 family (e.g., phenytoin, carbamazepine, rifampin, rifabutin, rifapentin, phenobarbital, and St. John's wort) may significantly decrease cabozantinib concentrations. The chronic use of strong CYP3A4 inducers should be avoided. Other drugs that induce CYP3A4 should be used with caution because these drugs have the potential to decrease exposure (AUC) to cabozantinib. Selection of alternate concomitant medications with no or minimal CYP3A4 enzyme induction potential is recommended. Caution must be used when discontinuing treatment with a strong CYP3A4 inducer in a subject who has been concurrently receiving a stable dose of cabozantinib, as this could significantly increase the exposure to cabozantinib.

Co-administration of cabozantinib with strong inhibitors of the CYP3A4 family (e.g., ketoconazole, itraconazole, clarithromycin, indinavir, nefazodone, nelfinavir, rand ritonavir) may increase cabozantinib plasma concentrations. Grapefruit and Seville oranges may also increase plasma concentrations of cabozantinib. Strong CYP3A4 inhibitors and other drugs that inhibit CYP3A4 should be avoided. Please refer to the drug interaction tables for lists of substrates, inducers, and inhibitors of selected CYP450 isozyme pathways:

http://www.fda.gov/Drugs/DevelopmentApprovalProcess/DevelopmentResources/DrugInteractionsLabeling/ucm080499.htm

Protein Binding: Cabozantinib is highly bound (approximately 99.9%) to human plasma proteins. Therefore, highly protein bound drugs (e.g., diazepam, furosemide, dicloxacillin, and propranolol) should be used with caution with cabozantinib because there is a potential displacement interaction that could increase free concentrations of cabozantinib and/or a co-administered highly protein-bound drug (and a corresponding increase in pharmacologic effect). Factors that influence plasma protein binding may affect individual tolerance to cabozantinib. A case of a drug-drug interaction between cabozantinib and warfarin that may involve displacement of plasma protein bound drug has been reported in the literature²². Because warfarin is a highly protein bound drug with a low therapeutic index, administration of warfarin at therapeutic doses is not allowed in subjects receiving cabozantinib due to the potential for a protein binding displacement interaction.

Other Interactions: In vitro data suggest that cabozantinib is unlikely to be a substrate for P-glycoprotein (P-gp), but it does appear to have the potential to inhibit the P-gp transport activity. Therefore, cabozantinib may have the potential to increase plasma concentrations of co-administered substrates of P-gp. Subjects should be cautioned regarding taking a P-gp substrate (e.g., fexofenadine, aliskiren, ambrisentan, dabigatran etexilate, digoxin, colchicine, maraviroc, posaconazole, ranolazine, saxagliptin, sitagliptin, talinolol, tolvaptan) while receiving cabozantinib.

Cabozantinib was shown to be a substrate of drug transporter MRP2 in an in vitro assay. Administration of MRP2 inhibitors to subjects may result in increases in cabozantinib plasma concentrations. Therefore, concomitant use of MRP2 inhibitors (e.g., cyclosporine, delaviridine, efavirenz, emtricitabine) should be approached with caution, and subjects taking MRP2 inhibitors should be monitored for AEs.

Concomitant administration of the proton pump inhibitor (PPI) esomeprazole resulted in no clinically-relevant effect on cabozantinib plasma PK in healthy volunteers. Therefore, concomitant use of gastric pH modifying agents (i.e., PPIs, H₂ receptor antagonists, and antacids) is not contraindicated in subjects administered cabozantinib.

Food Effects: As food increases exposure levels of cabozantinib, subjects should fast (with the exception of water) for at least 2 h before taking their dose of cabozantinib. After the 2-hour fast, subjects are to take cabozantinib with a full glass of water (minimum of 8 oz or 240 mL) with no more food intake for one hour post-dose.

6.2.2 Potential Drug Interactions

No drug interactions between cabozantinib and ipilimumab and nivolumab have been observed in previously reported clinical trials. Cabozantinib does not affect metabolism or the serum half-life of ipilimumab or nivolumab. Cabozantinib has overlapping toxicity with ipilimumab/nivolumab including the potential to cause diarrhea, elevated liver enzymes, skin rash, and hypothyroidism.

7 SAFETY

7.1 Adverse Events and Laboratory Abnormalities

7.1.1 Adverse Events (AEs)

An AE is any untoward medical occurrence in a patient or clinical trial subject who has been enrolled in a clinical study and who may have been administered an investigational product, regardless of whether or not the event is assessed as related to the study treatment. An adverse event can therefore be any unfavorable and unintended sign (including an abnormal laboratory finding), symptom, or disease temporarily associated with the use of an investigational product, regardless of whether or not the event is assessed as related to the investigational product. This requirement includes specific events or symptoms associated with cancer progression or general clinical deterioration to ensure potential toxicities are not overlooked. Radiographic progression without associated clinical sequalae is not considered an AE: terms such as 'disease progression' should be avoided. An adverse event can arise from any use of the drug (eg off-label use, use in combination with another drug) and with any route of administration, formulation, or dose, including an overdose. This definition also includes AEs associated with medication errors and uses of the investigational product outside what is in the protocol, including misuse and abuse. Pre-existing medical conditions that worsen during the study should be recorded as AEs. Abnormal laboratory values, ECG findings, or vital signs are to be recorded as AEs if they meet the criteria described in this protocol.

All untoward events that occur after start of study therapy through 30 days (100 days for SAEs and certain other events [See AEs of Special Interest Table]) after the last study treatment are to be recorded by the investigational site.

At each scheduled and unscheduled visit, AEs are to be identified and assessed based upon study procedures, routine and symptom-directed clinical investigations, and subject query/report.

Seriousness, severity grade, and relationship to study treatment will be assessed by the Investigator.

Severity grade will be defined by the current version of the National Cancer Institute (NCI)-Common Terminology Criteria for Adverse Events (CTCAE). This study will use the NCI CTCAE v5.0.

Assessment of the relationship of the AEs to individual study treatment by the Investigator is based on the following two definitions:

- Not Related: An event is assessed as not related to study drug if it is attributable to another
 cause and/or there is no evidence to support a causal relationship to the study treatment.
- Related: A related AE is defined as an AE where a causal relationship between the event and the study treatment is a reasonable possibility. A reasonable causal relationship is meant to convey that there are facts (e.g., evidence such as dechallenge/rechallenge) or other clinical arguments to suggest a causal relationship between the AE and study treatment. Possibly and probably related AEs should be documented as related.

Non-serious Adverse Events (AE) are to be provided to BMS in aggregate via interim or final study reports as specified in the ISR agreement or, if a regulatory requirement [eg, IND US trial] as part of an annual reporting requirement.

Non-serious AEs should be followed to resolution or stabilization, or reported as SAEs if they become serious. Follow-up is also required for non-serious AEs that cause interruption or discontinuation of study drug and for those present at the end of study treatment as appropriate.

7.1.2 Laboratory Abnormalities

All laboratory data required by this protocol and any other clinical investigations should be reviewed by the Investigator. Any abnormal value that leads to a change in subject management (e.g., dose reduction, delay, discontinuation, or requirement for additional medication or monitoring) or that is considered to be of clinical significance by the Investigator should be reported as an AE or SAE as

appropriate, unless this value is consistent with the subject's present disease state or is consistent with values obtained prior to entry to the study.

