4.2 Treatment Period

During the Treatment Period subjects will receive treatment for up to 24 months or until either disease progression, the occurrence of unacceptable drug-related toxicity or for other reason(s) for subject withdrawal as described in Section 2.1. Subjects should be instructed to immediately inform the Investigator of any AEs. Subjects experiencing dizziness, sleepiness, or other symptoms that could influence alertness or coordination should be advised not to drive or operate other heavy machinery.

Abnormalities in clinical laboratory tests that lead to a change in subject management (e.g., dose delayed [withheld] or reduced, requirement for additional medication, treatment or monitoring) are considered clinically significant and should be documented. If laboratory values constitute part of an CONFIDENTIAL - Cabozantinib + Nivolimab + Ipililumab Protocol Required Elements

event that meets criteria defining it as serious, the event (and associated laboratory values) must be reported as an SAE.

Regular tumor assessments should be performed to determine if PD is present. Tumor assessments should continue on the protocol-defined schedule, relative to the date of first dose of study treatment, regardless of whether study treatment is given, reduced, held or discontinued. The same imaging modalities used at screening will be used for subsequent tumor assessments after first dose.

If the subject is unable to have a study assessment taken within the defined time window due to an event outside of his or her control (e.g., clinic closure, personal emergency, inclement weather, vacation), the assessment should be performed as close as possible to the required schedule.

The Treatment Period ends when a subject receives his or her last dose of study treatment; the subject then enters the Post-Treatment Period.

The following schedule of assessments applies to all subjects. More frequent assessments should be obtained if clinically indicated.

Study Assessments

Study Day/Visit Day	Cycles 1-4 (21 days) Day 1 (+/- 4 days)	Cycles 5 + Day 1 (+/- 4 days)	Instructions
Adverse Event Assessment	Х	Х	
Concomitant Medications	х	х	Review of prohibited medications prior to each study drug dosing
Physical Exam	X	Х	
Vital Signs	х	х	Weight, blood pressure, pulse, 02 saturation, respirations at each visit
ECOG Performance Status	x	x	
Questionnaire(s)	Х	Х	FACT-M (Version 4)
Cabozantinib 40 mg PO daily Continuous	х	х	

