- Grade 3 drug-related endocrinopathies, adequately controlled with only physiologic hormone replacement;
- Grade 4 neutropenia ≤ 7 days;
- Grade 4 lymphopenia or leukopenia;
- Isolated Grade 4 electrolyte imbalances/abnormalities that are not associated with clinical sequelae and are corrected with supplementation/appropriate management within 72 hours of their onset;
- Grade 4 drug-related endocrinopathy AEs, such as, hyper- or hypothyroidism, or glucose
 intolerance, which resolve or are adequately controlled with physiologic hormone replacement
 (corticosteroids, thyroid hormones) or glucose-controlling agents, respectively, may not require
 discontinuation after discussion with and approval from the Principal Investigator;
- Dosing delays to allow for prolonged steroid tapers to manage drug-related adverse events are allowed. Drug-related adverse events are any toxicity temporally associated with administration of the investigational agent that may be at least possibly related to study treatment;

 Dosing delays lasting > 12 weeks from the previous dose that occur for non-drug-related reasons may be allowed if approved by the Principal Investigator.

Prior to re-initiating treatment in a participant with a dosing delay lasting > 12 weeks, the Principal Investigator must be consulted. Tumor assessments should continue as per protocol even if dosing is delayed. Periodic study visits to assess safety and laboratory studies should also continue as clinically indicated during such dosing delays.

5.4.3 Management of Hepatocellular Toxicity Associated with Cabozantinib and Nivolumab and Ipililumab

Elevations of aminotransferases (ALT and AST) and bilirubin have been observed during treatment with cabozantinib, anti-PD-(L)1 agents, and anti-CTLA-4 agents. It is recommended that subjects with elevation of ALT, AST, and/or bilirubin have more frequent laboratory monitoring of these parameters. If possible, hepatotoxic concomitant medications should be discontinued in subjects who develop increased values of ALT, AST, or bilirubin, and other causes (e.g., cancer-related, infection) should be evaluated.

The following condition requires discontinuation of all study drugs:

 Drug-related ALT or AST > 3x ULN in combination with total bilirubin > 2x ULN without reasonable other explanation, consistent with drug-induced liver injury (DILI).

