Using the safety evaluable analysis set, the incidence of having Grade ≥ 3 AEs will be determined for study participants that received at least one dose of their assigned treatment. The point estimate and 95% confidence interval will be reported.

For correlative molecular profiling endpoint, paired t-test or Wilcoxon signed-rank test will be performed to evaluate tumor infiltrating immune cell profiling and gene expression changes between pre- and post-treatment.

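### Section 7.1.2 lets a Grade ≥3 or management-changing laboratory value stay off the AE record as disease-consistent without a judgement that it is unrelated to study drug, so the Grade ≥3 rate can be undercounted.

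*Combined protocol and SAP*

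**What the plan says.** Section 7.1.2 sets the trigger for reporting laboratory values: "Any abnormal value that leads to a change in subject management", or any value the investigator considers clinically significant, is reported as an AE or SAE. One exemption covers the whole sentence: "unless this value is consistent with the subject's present disease state or is consistent with values obtained prior to entry to the study".

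Section 7.1.1 bears on this in four ways:
- On laboratory values it defers to the protocol's own criteria: "Abnormal laboratory values, ECG findings, or vital signs are to be recorded as AEs if they meet the criteria described in this protocol".
- On disease-related events generally it is inclusive: "This requirement includes specific events or symptoms associated with cancer progression or general clinical deterioration to ensure potential toxicities are not overlooked".
- It asks for a condition present at entry to be recorded as an AE if it gets worse.
- On causality it says: "Possibly and probably related AEs should be documented as related".

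Section 4.2 says that laboratory abnormalities that change management "are considered clinically significant and should be documented", with no exemption for disease.

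The two statements of the safety outcome differ. Endpoint 5 in Section 2 counts Grade ≥3 treatment-related events. In Section 8, "the incidence of having Grade ≥ 3 AEs will be determined for study participants that received at least one dose of their assigned treatment", with no filter on relatedness.

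**The concern.** Being consistent with disease is a weaker test than being unrelated to drug, because a value can be both consistent with metastatic melanoma and possibly caused by treatment. Section 5.4.3 acknowledges the overlap for the liver: ALT, AST and bilirubin elevations occur with all three drug classes, and "other causes (e.g., cancer-related, infection) should be evaluated". Section 5.4.1.2 lists anemia, raised ALP and hyponatremia among cabozantinib laboratory events, and each is also plausible in metastatic cancer.

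Under Section 7.1.2 as worded, such a value can be set aside as disease before an AE entry exists, and the possibly-related rule applies only to AEs. The trial is single-arm and relatedness is judged by the investigator, so no comparison group would reveal the loss. At stake is a one-directional error in the Grade ≥3 rate of a new triplet.

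**Working it through.** The documents give no expected Grade ≥3 rate and no safety threshold, so there is no plan figure to reproduce. The check is mainly one of wording.

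**Step 1: does another rule override the exemption?**
- Section 7.1.1 on laboratory values does not. It refers back to the protocol's criteria, which for laboratory values are those of 7.1.2.
- Section 7.1.1 on progression-associated events and on worsening conditions points the other way, but does not say that it prevails.
- Section 4.2 requires documentation and does not name AE recording.
- The sections therefore conflict without a stated order, and two coordinators could code the same value differently.

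**Step 2: what is captured by another route?**
- Section 7.3 makes potential DILI and hepatitis, including AST/ALT above 10x ULN, AESIs that are recorded and reported whether or not serious. Section 7.2.2 also puts potential DILI on the SAE timeline.
- Section 4.2 separately requires laboratory values that form part of a serious event to be reported as an SAE.
- Section 3.1 caps entry AST and ALT at 3x ULN, so a value above 5x ULN can hardly match a pre-entry value. For the transaminases only the disease-state limb matters.

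**Step 3: what remains?**
- AST/ALT above 5x and up to 10x ULN, or an isolated bilirubin elevation, not diagnosed as hepatitis or DILI and attributed to disease. The severe row of the Section 5.4.3 table starts at AST/ALT above 5x ULN or bilirubin above 3x ULN, so this range is not trivial.
- Non-liver values such as anemia, ALP and electrolytes, which Section 7.3 does not name. Section 5.4.1.2.20 notes that some electrolyte abnormalities with cabozantinib were Grade 3 or 4.

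**Step 4: size per patient.** The rate is x/n. One patient whose only Grade ≥3 event is exempted lowers it by 1/n: 1/25 = 4.0 points, or 1/41 = 2.4 points if the trial expands.

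**Step 5: illustration.** The counts are assumptions. The exact (Clopper-Pearson) 95% limits are the 0.025 quantile of Beta(x, n − x + 1) and the 0.975 quantile of Beta(x + 1, n − x).

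| True cases | Missed | Reported | 95% CI |
|---|---|---|---|
| 12/25 | 0 | 48.0% | 27.8–68.7 |
| 12/25 | 1 | 44.0% | 24.4–65.1 |
| 12/25 | 2 | 40.0% | 21.1–61.3 |
| 12/25 | 3 | 36.0% | 18.0–57.5 |
| 20/41 | 0 | 48.8% | 32.9–64.9 |
| 20/41 | 2 | 43.9% | 28.5–60.3 |

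Across other assumed rates at n = 25, two missed patients move 40.0% to 32.0% (10 to 8 cases) or 60.0% to 52.0% (15 to 13 cases).

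**The case against.** A reader might infer that dose-changing, possibly drug-related liver toxicity simply goes unrecorded and its relatedness is never assessed. The documents do not support that.
- **Dosing rules.** Sections 5.4.2.1 and 5.4.2.3 tie IO delay or discontinuation for liver values to drug-relatedness, and the cabozantinib modification table in 5.4.1 is for treatment-related AEs. Section 5.4.2.3 describes drug-related events as those at least possibly related. A liver value that changes dosing under these rules has already been judged at least possibly related, and it would be inconsistent then to exempt it as disease.
- **AESI list.** Section 7.3 makes the liver the best-protected organ here. It also names nephritis, pancreatitis, myopathies and several endocrinopathies.
- **Data retention.** Section 9 has all study data entered on eCRFs. An exempted value is missing from the AE list, not necessarily from the database.
- **Endpoint 5.** A value truly caused by disease does not belong in a treatment-related count, so leaving it out is correct.

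All four points stand and narrow the concern. They do not close it. Section 5.4.2.1 also allows a discretionary delay for any laboratory abnormality with no relatedness judgement, and 7.1.2 counts added medication or monitoring as a change in management. The Section 8 incidence is an incidence of AEs, and the plan does not say that it will be supplemented by grading the laboratory data.

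**Conclusion.** The point holds in limited form. As worded, Section 7.1.2 allows a Grade ≥3 or management-changing value to be left off the AE record without a finding that it is unrelated to study drug, and it does not sit with Section 7.1.1. The Section 8 incidence loses any patient whose only Grade ≥3 event is exempted. Endpoint 5 loses only those whose exempted value was possibly related. Exemption can only remove cases from the Section 8 count, so any error there is downward.

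It would go too far to conclude that the rate **is** undercounted, or that the liver is the most exposed organ. How many values would be exempted cannot be derived from the documents, and the counts in the illustration are assumed. With two missed patients the intervals overlap heavily, and no decision rule depends on this rate. This is a cheap improvement in recording, not a flaw that undermines the trial.

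**What to change.** In Section 7.1.2, limit the exemption to values that have not worsened in CTCAE grade from baseline **and** led to no change in management. Record as an AE, with the investigator's relatedness judgement, every other value that is Grade ≥3, that has worsened and is clinically significant, or that changed management. Align Section 7.1.2 with Sections 4.2, 7.1.1 and 7.3 so that one rule governs laboratory values.

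The cost is a wording amendment, a few more laboratory AE entries (some finally judged unrelated) and a slightly less favourable Grade ≥3 rate. The change concerns recording only; no dosing or management rule is altered.
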